## **Background**

The current FDA approved evidence base for the treatment of bipolar depression is limited to three atypical antipsychotics, one of which is paired with an SSRI. (Nierenberg et. al. 2015). The data analyzed from the STEP-BD study supports the notion that the use of antidepressants added to mood stabilizers provides no improved outcome but may carry the risk of precipitating or supporting a mixed or manic episode. (Sachs et. al., 2007, El-Mallakh et. al. 2015) A problem in developing safe and effective treatment paradigms for bipolar depression is that the population is so heterogeneous and subgroups may require different pharmacological interventions (Altshuler et. al. 2003, Goldberg et. al. 2015)

Transcranial magnetic stimulation has had a growing impact on the treatment of major depressive disorder. There is increasing use of this modality as insurers have increasingly provided support. Sheppard Pratt has been a leader in the adoption of TMS and our clinical TMS program using the Neuronetics NeuroStar

TMS Therapy® System (See Appendix 1) has treated over 200 patients over the past six years. While there is a clear evidence base for the use of TMS in MDD, there is as yet only a small anecdotal base for its use in bipolar depression (Connolly 2012, Nola 2013, Woźniak-Kwaśniewska 2015).

We are currently doing a retrospective look at our experience in treating bipolar depression with TMS which has represented about 15% of our patient base. ([name] data in review) A preliminary evaluation of our database shows that we have treated 45 patients with bipolar depression (See Appendix 2). Four patients had their course stopped by their clinician due to side effects; none of them met the criteria for mania or mixed state. Five patients had their course completed by a different TMS provider (closer to their home) and two had incomplete data. For the 34 patients who completed a course of treatment, 26 (76.5%) met response criteria by Montgomery-Asberg Depression Rating Score (MADRS) score and 12 met remission criteria (35%). These results are numerically superior to our experience in unipolar depression where our response rate is 62% and our remission rate is 31%. In general the treatment has been well tolerated and effective. Most of these patients have a long history of either poor efficacy or safety in the use of antidepressants and inadequate antidepressant response to the use of mood stabilizers or atypical antipsychotics.

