### **Study Overview and Hypotheses**

We propose to screen patients with bipolar depression I or II, who are already on acceptable mood stabilization. They may or may not be on antidepressants at the time of screening but subjects on antidepressants would be taken off them before completing the screening phase. Those patients who have a depression of at least moderate severity without significant symptoms of activation or mania will be started on a course of open label TMS treatment of up to 35 sessions. Safety and efficacy assessments will be done weekly. Patients will complete a course of treatment when they meet remission criteria (MADRS score < 10) or at the end of 30 treatments, whichever comes first. Patients who are still judged to be improving between treatment 25 and treatment 30 will be eligible to complete up to five additional treatments as the discretion of each site's principal investigator.

Patients who meet response criteria (MADRS score decreases by at least 50%) will complete the full course of 30 to 35 TMS sessions. Patients will be withdrawn for safety concerns, particularly the onset of activation suggestive of mania or a mixed state.

Patients who meet response or remission criteria will be followed monthly for up to six months to evaluate the durability of response. They will be on standard mood stabilizing medications and psychotherapy per their clinician's discretion.

The primary study hypotheses are:

1. TMS will provide effective antidepressant treatment in patients with bipolar depression both type I and II.
2. TMS will show a shorter time to response in bipolar depressed patients compared with the available data in unipolar depressed patients.
3. TMS can be safely given in bipolar depression without inducing a manic or mixed episode switch in patients who are receiving adequate concurrent mood stabilizing medication

The secondary hypothesis is:

1. The majority of treatment responders will show adequate durability of response with remitters showing better durability.

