### Phase II: Open Label TMS Treatment

Once study patients are on stable medication and it is confirmed that they meet the entry criteria for Phase II they will begin a standard course of five times a week TMS treatment for six weeks. They will be assessed at each treatment visit for side effects, concomitant medication use, and once per week for severity of depression and evidence of any symptoms suggestive of mania or agitation. Any suggestion of mania or activation will be assessed by the study physician who will evaluate to determine if the subject can remain in the study or needs other intervention to manage emerging symptoms.

The MADRS, the 17-item Hamilton Depression Rating Scale (HAM-D17), the Quick Inventory of Depressive Symptomatology (Self-Report) (QIDS-SR16), the

YMRS, the C-SSRS (Columbia Suicide Severity Rating Scale) and CGI-S will be performed once per week. The CGI-Improvement Scale (CGI-I) will be done weekly starting at Visit 3. Treatment will continue until remission criteria is reached (MADRS score <10) or 30 treatments have occurred, whichever comes first. If improvement is continuing between treatment 25 and 30, treatments may be extended up to 35. Patients who are discontinued due to onset of manic or mixed symptoms will be followed until resolution of these symptoms. Patients who meet response criteria (MADRS score drops by at least 50%) or remission criteria will be followed in Phase III.

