### **Inclusion and Exclusion Criteria – Phase II**

Patients must meet fulfill all of the following inclusion criteria in order to enter Phase II of the study:

1. Must be at least 18 years old.

2. Must meet **DSM-5** criteria for bipolar (either I or II) depression by clinical interview and M.I.N.I. The duration of the current depressive episode must be at least 4 weeks and no longer than 3 years in length.
3. Should have a MADRS score of at least 20 at screening, an YMRS score of less than 12 and a CGI score of at least 4.
4. Must have signed the informed consent document and have a level of understanding sufficient to provide informed consent and to communicate with the investigator and site personnel.
5. Must be on a mood stabilizer acceptable to the study physician which is consistent with their diagnosis. The mood stabilizer must be at a stable dose for at least four days before starting TMS treatment.
6. If female of childbearing potential, patients must
  - a) have a negative urine pregnancy test at screening, and
  - b) not be nursing or planning a pregnancy, and
  - c) be on a medically acceptable method of birth control acceptable to the principal investigator.

Choices of contraception that meet the study requirements are

- Intrauterine device
- Hormonal contraception (estrogen-containing birth control pills, Vaginal ring, patch, injections or implants)
- Latex condom with spermicide
- Diaphragm with spermicide
- Cervical cap with spermicide

Females of childbearing potential who are abstinent can enroll in the study.

Patients will *not* be enrolled in Phase 2 of the study if they meet any of the following exclusion criteria:

1. May not be directly affiliated with Sheppard Pratt Clinical Research Programs or be immediate family of Research Programs personnel.
2. Must not have another primary Axis I diagnosis.
3. The subject must not have stopped an antidepressant less than two weeks before starting TMS treatment or unable to discontinue antidepressant therapy.
4. Should have no previous history of psychosis or substance dependence or abuse within the six months prior to Screening

5. Presence of an Axis II disorder felt by the investigator to potentially interfere with study compliance would exclude a potential participant.
6. Should not have prior intolerance of TMS or significant lack of response to adequate trials of TMS.
7. Should not have a lifetime history of lack of response to ECT or VNS.

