### **Statistical Methods**

- Sample Size

We are looking to collect sufficient data to demonstrate the efficacy and safety of TMS in bipolar depression. As this is an open label trial we will aim to treat 30 patients to achieve a reasonable sample size.

- Primary Efficacy Analysis

The primary outcome measure will be the percentage of patients who respond or remit after 30 to 35 treatments. We will subdivide patients based on the diagnosis of either bipolar I or bipolar II to compare effectiveness between those groups.

The other primary outcome will be the percentage of patients who meet criteria for onset of manic symptoms based on the YMRS. The patients will also be separated based on their diagnostic category.

- Secondary Efficacy Analysis

We will also look at the HAM-D and CGI to see the percentage of patients meeting response criteria.

For the patients meeting remission criteria, we will calculate the number of treatments required to achieve remission. Patients who only meet response criteria will be treated for 30 to 35 sessions.

Responders and remitters will also be followed for six months after the final treatment to see the durability of response. Percentage of patients' meeting relapse criteria will be calculated.

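### The hypothesis of a shorter time to response than in unipolar depression has no planned analysis, and sessions to remission in remitters cannot stand in for one

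*Combined protocol and SAP*

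**What the plan says.** In Study Overview and Hypotheses, a list introduced by "The primary study hypotheses are" has as its second item "TMS will show a shorter time to response in bipolar depressed patients compared with the available data in unipolar depressed patients". The same statement is in Aims and Hypotheses, there as a specific hypothesis below two primary aims (effectiveness and safety).

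The Statistical Methods section plans five kinds of result:

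- the percentage responding or remitting by the end of the course, split by bipolar I and II;
- the percentage with onset of manic symptoms on the YMRS, split the same way;
- the percentage responding on the HAM-D and CGI;
- a timing summary: "For the patients meeting remission criteria, we will calculate the number of treatments required to achieve remission";
- the percentage relapsing during the six-month follow-up.

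For patients who respond without remitting, the section says only that they go on to 30 to 35 sessions. The Primary Efficacy Measure section adds MADRS change from baseline to endpoint.

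On reference data, Background gives the site's unipolar experience as "our response rate is 62% and our remission rate is 31" (percent), with no times. On the site's bipolar series it says "For the 34 patients who completed a course of treatment, 26 (76.5%) met response criteria", and that 12 remitted.

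The raw material for a time to response is collected: "Safety and efficacy assessments will be done weekly". The event is also defined, in Phase II: "Patients who meet response criteria (MADRS score drops by at least 50%) or remission criteria will be followed in Phase III".

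**The concern.** The hypothesis has three parts: an event (response), a time to that event, and a comparison with unipolar patients. The analysis section takes up the event only as an end-of-course percentage, and it has neither the time nor the comparison. The one time it does plan is for remission.

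If the plan is followed as written, a hypothesis listed as primary gets no answer. A statement that bipolar patients respond faster than unipolar patients could then rest on an event, a denominator and a reference chosen after results are seen. With no concurrent control, those choices could decide the conclusion.

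**Working it through.** **1. Hypothesis against plan**

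| Element | Hypothesis | Statistical Methods |
|---|---|---|
| Event | Response: MADRS fall of at least 50% | For timing, remission only: MADRS below 10 |
| Patients | Bipolar depressed patients | Remitters only |
| Time | Time to response | Sessions to remission |
| Comparator | Unipolar data, not identified | None |
| Method | Shorter than the comparator | None |

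The rows differ in event, patients and comparison. The planned summary omits patients who do not remit instead of keeping them in the denominator.

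**2. Background figures reproduced**

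45 treated − 4 stopped for side effects − 5 completed elsewhere − 2 with incomplete data = 34. Response 26/34 = 76.5%. Remission 12/34 = 35.3%, printed as 35%. Both agree with the document.

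**3. Responders left untimed in that series**

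Assuming every remitter is also a responder: 26 − 12 = 14, and 14/26 = 53.8%.

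**4. Projection to this trial**

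The assumption is that the retrospective rates carry over. N is 30 in Statistical Methods, and 30 + 20 = 50 across both sites in Study Population. The rates are taken first on the 34 completers, then on all 45 treated with the other 11 counted as neither responders nor remitters.

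| Denominator | Timed (remitters) | Of 30 | Of 50 | Responders untimed | Of 30 | Of 50 |
|---|---|---|---|---|---|---|
| 34 completers | 12/34 = 35.3% | 10.6 | 17.6 | 14/34 = 41.2% | 12.4 | 20.6 |
| 45 treated | 12/45 = 26.7% | 8.0 | 13.3 | 14/45 = 31.1% | 9.3 | 15.6 |

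**5. Why baseline has to be defined**

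The entry rule is "Should have a MADRS score of at least 20 at screening", and screening can last up to 28 days. At a baseline of 20, the highest remitting score of 9 is a fall of (20 − 9)/20 = 55%, so remission implies response. If the score has dropped to 17 before the first session, a score of 9 is a fall of (17 − 9)/17 = 47%: remission without response.

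**6. Precision of a response proportion at any one week**

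Clopper-Pearson 95% intervals: 15/30 gives 31.3% to 68.7%; 25/50 gives 35.5% to 64.5%.

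**The case against.** The best case against the point is about weight. The two primary aims are effectiveness and safety, the two primary outcomes match them, and both are untouched. The time-to-response hypothesis is called primary only in the Study Overview list. The trial is small and open-label, the MADRS is rated weekly, and the 50% criterion is defined, so the variable can be derived at any time. All of this stands, and it limits the harm. It does not supply the missing definition, denominator or reference, which protect the claim only if fixed before outcomes are examined.

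A reader might also infer four stronger things that the documents do not support.

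- **The data cannot answer the hypothesis.** They can yield a time to response; the gap is in the analysis and the reference.
- **The choices will be made after the results.** The plan leaves them open. Nothing shows when they would be made, so only *could* is justified.
- **The protocol holds no unipolar timing data.** The appendices are listed by title only. Appendix 2's title concerns bipolar depression, but Appendix 1 is prescribing information for a device approved for major depressive disorder, and its contents are not shown. Only the visible text can be said to lack a reference.
- **Sessions to remission are faulty because they depend on baseline severity.** The 50% criterion depends on it too: at baselines of 20, 30 and 40 it needs falls of 10, 15 and 20 points. The argument cuts both ways, and I do not rely on it.

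**Conclusion.** The point holds. A hypothesis listed as primary has no planned time-to-response variable and no planned comparison, and the visible text names no unipolar timing reference. The planned sessions-to-remission summary is not a substitute, because it times another event in patients selected by that event.

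In the site's own series the summary would miss 14 of 26 responders (54%), if remitters are a subset of responders. If those rates carried over, about 8 to 11 of 30 patients (13 to 18 of 50) would supply a time and about 9 to 12 responders (16 to 21) would supply none. The lower figures use all 45 treated patients and the higher figures the 34 completers. The carry-over is an assumption; the trial's own rates may differ.

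This does not undermine the response or mania results. It is a cheap improvement to the plan.

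**What to change.** In Statistical Methods:

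- Define time to response as the treatment week of the first weekly MADRS rating that shows a fall of at least 50% from baseline, in all treated patients through the end of Phase II. Baseline is the last MADRS before the first TMS session.
- Use treatment week as the only time scale.
- Count patients who withdraw before response as non-responders at all later weeks.
- State that a patient who remits from a low baseline without a 50% fall has not met this event.
- Report the cumulative proportion responding at each week with 95% confidence intervals, and the median if it is reached.
- Before outcomes are examined, name a unipolar reference with the same response definition, a comparable rating schedule, an all-treated denominator and the same horizon.
- Keep sessions to remission as a descriptive result.

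If no such reference exists, label the hypothesis exploratory in Aims and Hypotheses and in Study Overview and Hypotheses, and make no claim of shorter time.

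The cost is some wording, one extra analysis of data already collected, and the work of finding the reference. The comparison stays external and non-randomised. It also stays imprecise: an observed 50% at n = 30 carries an interval of 31% to 69%. The claim of a shorter time may be lost.

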### Open Label Treatment with TMS

Stimulation will occur over the left dorsolateral prefrontal cortex at 120% magnetic field intensity relative to the subject’s resting motor threshold, at 10 pulses per second for 4 seconds, with an off time, or intertrain interval, of 26 seconds. Repositioning of the coil, per the NeuroStar User Manual, and prophylactic use of acetaminophen or ibuprofen will be allowed for subjects reporting sensations at or near the stimulation site which are uncomfortable or painful. During the first week of treatment only, in the event that the subject cannot tolerate the treatment at these dose parameters, dose intensity may be titrated downward to 110% of the motor threshold, with all other dose parameters remaining the same. Treatment sessions will last for 37.5 minutes (75 trains) to provide a total of 3,000 pulses per treatment session. All qualified study patients will receive open label TMS treatment, five times a week for a total of 30 treatments or until they meet remission criteria.

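### Treatments to remission is counted only in remitters and only to the nearest weekly rating, so it does not show how many sessions remission takes among patients who start TMS

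*Combined protocol and SAP*

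**What the plan says.** The Secondary Efficacy Analysis in Statistical Methods plans one result about speed or amount of treatment: "For the patients meeting remission criteria, we will calculate the number of treatments required to achieve remission". It does not define the count, name a summary statistic or interval, or say what happens to patients who do not remit or who leave early.

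The surrounding design is as follows.

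- **Schedule.** Phase II is a "standard course of five times a week TMS treatment for six weeks". Treatment Compliance sets four sessions a week as the minimum.
- **Ratings.** The Study Overview says "Safety and efficacy assessments will be done weekly". Phase II says patients are assessed "once per week for severity of depression and evidence of any symptoms suggestive of mania or agitation".
- **Stopping.** "Treatment will continue until remission criteria is reached (MADRS score <10) or 30 treatments have occurred, whichever comes first". The course can run longer: "If improvement is continuing between treatment 25 and 30, treatments may be extended up to 35".

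**The concern.** There are two distinct limitations, with different causes.

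1. **Coarse timing.** A MADRS below 10 can be seen only at a weekly rating. The session at which the score first fell below 10 lies somewhere among the 4 or 5 sessions since the previous rating. The count at the detecting rating is the upper end of that interval.
2. **Conditioning on success.** Patients who reach 30 to 35 sessions without remission, or who are withdrawn, contribute nothing. The result is bounded by the course length and describes timing among those who succeeded.

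What is at stake is how the number is read. One of the stated hypotheses concerns faster response than in unipolar depression, yet Statistical Methods gives no time-to-response analysis. The remission count is the only speed result planned for the treatment phase, so a reader may take it as the number of sessions a bipolar patient needs. A remitters-only count cannot carry that meaning.

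**Working it through.** **Figure in the protocol.** The plan gives no target for treatments to remission. The only related figure is the remission rate in the site's retrospective bipolar series (Background). Completers: 45 − 4 − 5 − 2 = 34. Remission: 12/34 = 35.3%, which reproduces the stated 35%.

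**Rating lag.** Assume the rating follows the last session of the week and onset is equally likely at each session. The schedule table is not in the text available, so the rating day is an assumption.

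- Five sessions a week: (4 + 3 + 2 + 1 + 0)/5 = 2.0 sessions too high, range 0 to 4.
- Four sessions a week: (3 + 2 + 1 + 0)/4 = 1.5.

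**Remitters-only mean against all-treated mean.** Assume a constant remission chance per session, a 30-session course and a rating after every fifth session. R is the proportion remitting by session 30; 70% is simply a doubling of 35%.

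- Per-session chance: h = 1 − (1 − R)^(1/30). True mean in remitters = 1/h − 30(1 − R)/R.
- Per-week chance: H = 1 − (1 − R)^(1/6). Observed mean in remitters = 5 × [1/H − 6(1 − R)/R].
- Restricted mean over all treated, with non-remitters counted at 30: R × observed mean + (1 − R) × 30.

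| | R = 35.3% | R = 70% | Shift |
|---|---|---|---|
| True mean, remitters | 14.42 | 12.56 | 1.9 |
| Observed mean, remitters | 16.45 | 14.64 | 1.8 |
| Observed median, remitters | 15 | 15 | 0 |
| Restricted mean, all treated | 0.353 × 16.45 + 0.647 × 30 = 25.22 | 0.70 × 14.64 + 0.30 × 30 = 19.25 | 6.0 |

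At 35.3% the observed mean exceeds the true mean by 16.45 − 14.42 = 2.0 sessions, matching the direct lag calculation.

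**Sensitivity to the model.** The decline models are simulations with assumed inputs: baseline MADRS mean 30, SD 5, floored at 20; rating error SD 3; between-patient SD of 2 points a week (linear slope) or 12 points (exponential six-week change).

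| Model | Remission rate | Observed mean, remitters | Restricted mean, all treated |
|---|---|---|---|
| Constant chance, 35-session cap | 35% to 70% | 18.76 to 16.64 (shift 2.1) | 29.27 to 22.15 (7.1) |
| Linear decline | 37% to 78% | 23.08 to 20.14 (2.9) | 27.43 to 22.26 (5.2) |
| Exponential decline | 40% to 81% | 17.82 to 14.40 (3.4) | 25.17 to 17.37 (7.8) |
| Fixed 50% pool of potential remitters, half-time to remission 30 to 5 sessions | 25% to 49% | 15.83 to 9.52 (6.3) | 26.46 to 19.92 (6.5) |

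In the last row speed among potential remitters is what varies, and the remitters-only mean follows it closely.

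**Precision.** With 30 patients, 0.353 × 30 = 10.6 remitters. The observed count has SD 8.5 under the constant-chance model, so the 95% half-width is 1.96 × 8.5/√10.6 = 5.1 sessions. Adding the 20 patients planned at the second site gives 0.353 × 50 = 17.6 remitters and a half-width of 1.96 × 8.5/√17.6 = 4.0. The 35% rests on completers; 12/45 would give 8 remitters among 30, though 7 of the 45 finished elsewhere or had incomplete data.

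**The case against.** The case for leaving the sentence alone has real force.

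- **The figure can be derived.** A reader might infer that weekly rating makes the count impossible. It does not: remission is an operational criterion, treatment stops once it is met, and sessions up to the first rating below 10 can be counted. The limit is one of resolution.
- **Insensitivity is not general.** A reader might infer that the figure hardly reflects how well TMS works. The documents do not support that as a general statement. The 1.8-session shift belongs to a constant-chance model, which makes the first session the likeliest one for remission although entry requires a MADRS of at least 20. The decline models give about 3 sessions, and the fixed-pool model gives 6.3. Any insensitivity comes from restricting to remitters, not from weekly rating.
- **The plan does not oversell it.** The sentence openly limits itself to remitters. It is a secondary description; efficacy rests on the percentage who respond or remit, and the speed hypothesis concerns response. That someone would misread the number is an inference.
- **The bias is smaller than the noise.** A 2-session lag is less than a half-width of 4 to 5 sessions.

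All four points stand and keep this from being a serious defect. They do not supply the missing definition or a rule for patients who never remit. Part of the all-treated mean's larger shift arises because it includes the remission rate, which is reported anyway; but sessions to remission among starters depends on that rate.

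**Conclusion.** The concern holds in a limited form. As planned, the count is known only to within 4 or 5 sessions, runs about 2 sessions high on average at five a week (1.5 at four), and describes when remitters remit. It does not give the number of sessions remission takes among patients who start TMS. Under a constant per-session chance, doubling remission from 35% to 70% moves the observed remitters-only mean by about 1.8 sessions, against about 6 for the all-treated restricted mean. That contrast depends on the model, and the remitters-only figure does respond to speed among remitters.

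The 35% comes from the site's completers. The 70%, the decline parameters, the fixed pool and the rating day are assumptions. The primary outcome is untouched. This is an inexpensive improvement to a secondary summary.

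**What to change.** In the Secondary Efficacy Analysis, replace the sentence with the following elements.

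- **Main display.** Cumulative incidence of remission (first weekly MADRS below 10) by sessions delivered, in all patients who start TMS. Place onset in the interval between the last rating of 10 or above and the first below 10.
- **Completers without remission.** Keep them in the denominator as non-remitters.
- **Withdrawals for manic or mixed symptoms or other safety reasons.** Count them as not remitting, as a competing event. Treating them as non-informatively censored would overstate cumulative remission, and manic onset is itself the other primary outcome.
- **Other withdrawals.** State the rule in advance, for example censoring at the last rating, with a repeat analysis counting them as not remitting.
- **Remitters-only count.** Keep it as descriptive, defined as sessions delivered up to the first weekly MADRS below 10, and report it with its interval and the number of remitters.

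The cost is new wording and slightly more analysis work. The weekly MADRS and the sessions delivered come from visits already planned, and no treatment or visit changes. The drawback is a less tidy result: the treatment number becomes a range.

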### Phase III: Six Month Follow Up

Patients' meeting response or remission criteria will be followed monthly for up to six months by in-person visits or phone interviews. The MADRS, CGI-S and CGI-I scales will be administered at each encounter. Relapse will be defined as a MADRS score of 20 or above for two consecutive weeks. Patients who meet relapse criteria will have an early termination visit the following week and referred for standard clinical treatment.

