### **Study Population**

It is estimated that up to approximately 30 patients will participate in the study at the Sheppard Pratt site with 20 additional patients enrolling at the Mayo Clinic Rochester site. Patients must have Bipolar I or Bipolar II depression as defined by the Diagnostic and Statistical Manual of Mental Disorders (DSM-5 criteria) and be taking a mood stabilizer acceptable to the principal investigator. They will not be allowed to take antidepressant medication. Their depression must be at least moderate in severity without significant symptoms of activation or mania.

Patients treated may come from the Retreat assisted living, outpatient services, outpatient practices of local psychiatrists, the Sheppard Pratt day hospital, or inpatient units. Patients enrolled at Mayo Clinic will come from their Mood program, Mood Clinic, Inpatient practice and the community. It is unlikely that current inpatients will qualify for this study as most of them will have co-morbidities, psychotic symptoms or mixed presentations which would exclude them.

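### The secondary hypothesis says remitters hold their response better, but the plan states only one relapse percentage for remitters and other responders together, and monthly contacts do not match the two-week relapse rule (minor)

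*Combined protocol and SAP*

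**What the plan says.** - **Hypothesis** (Study Overview and Hypotheses). The single secondary hypothesis is: "The majority of treatment responders will show adequate durability of response with remitters showing better durability". The first part concerns all responders. The second compares two groups.
- **Analysis** (Statistical Methods, Secondary Efficacy Analysis). Responders and remitters are followed for six months after the last treatment, and then: "Percentage of patients' meeting relapse criteria will be calculated". Nothing is said about reporting by remission status or about an interval.
- **Splits made elsewhere in the same section.** Both primary outcomes are divided by bipolar I and II. For number of sessions, the section treats remitters apart from the rest: "Patients who only meet response criteria will be treated for 30 to 35 sessions".
- **Treatment length** (Open Label Treatment with TMS). Stimulation is given "five times a week for a total of 30 treatments or until they meet remission criteria", so remitters can stop early.
- **Relapse rule and visits** (Phase III: Six Month Follow Up). "Relapse will be defined as a MADRS score of 20 or above for two consecutive weeks". Patients "will be followed monthly for up to six months by in-person visits or phone interviews". A patient who relapses has an early termination visit one week later. Patient Withdrawal requires a MADRS at that visit.

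**The concern.** A claim that one group does better than another needs a result for each group. The durability sentence yields a single figure, and the section on Phase III entry adds no analysis. Followed as written, the plan leaves half of the only secondary hypothesis without an answer. The split could be made at reporting, since MADRS is held per patient. In an open-label study, though, the handling of lost patients and the point at which response is judged would then be settled after results are known.

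The relapse rule has its own difficulty. Two successive weeks at 20 or above cannot be read from ratings about a month apart, so relapse as defined may go unrecorded in either group.

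**Working it through.** The plan gives no relapse rate, precision target or power for this outcome, so there is no stated figure to reproduce. The Background rates do check: 26/34 = 76.5% and 12/34 = 35.3%.

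**Inputs.** From Background: 26 responders and 12 remitters among 34 completers, and 45 bipolar patients treated in all. From Statistical Methods: 30 to be treated. From Study Population: about 30 at one site, "with 20 additional patients enrolling at the Mayo Clinic Rochester site", so 50 in total. Assumptions: the 12 remitters are among the 26 responders, leaving 26 - 12 = 14 with response only; relapse is 30%, varied from 20% to 40%.

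**1. Expected group sizes.**

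| Treated | Denominator | Remitters | Response only |
|---|---|---|---|
| 30 | 34 completers | 30 × 12/34 = 10.6, about 11 | 30 × 14/34 = 12.4, about 12 |
| 50 | 34 completers | 50 × 12/34 = 17.6, about 18 | 50 × 14/34 = 20.6, about 21 |
| 30 | all 45 treated | 30 × 12/45 = 8.0 | 30 × 14/45 = 9.3, about 9 |

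**2. What one combined figure leaves open.** With R relapses in total, the difference (remitters minus response only) can lie anywhere from 0/n1 - R/n2 to R/n1 - 0/n2.

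| Overall | Lowest | Highest |
|---|---|---|
| 5/17 | 0/8 - 5/9 = -55.6 points | 5/8 - 0/9 = +62.5 points |
| 7/23 | 0/11 - 7/12 = -58.3 points | 7/11 - 0/12 = +63.6 points |
| 12/39 | 0/18 - 12/21 = -57.1 points | 12/18 - 0/21 = +66.7 points |

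These are logical limits, not likely values. They show that the combined figure does not fix even the direction.

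**3. Precision of a split.** With the same relapse rate p in both groups, the approximate 95% half-width is 1.96 × √[p(1-p)(1/n1 + 1/n2)].

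- p = 0.3: 43.6 points for 8 v 9; 37.5 for 11 v 12; 28.9 for 18 v 21.
- Across the range: 25.2 points (p = 0.2, 18 v 21) to 46.7 (p = 0.4, 8 v 9).
- Exact (Clopper-Pearson) intervals within a group: 2/11 = 18% (2% to 52%); 4/12 = 33% (10% to 65%); 4/18 = 22% (6% to 48%); 6/21 = 29% (11% to 52%).
- If relapse were 20% v 40%, a two-sided Fisher test at 5% would have about 11% power (11 v 12) or 22% (18 v 21).
- One patient lost to follow-up moves a group's percentage by between 1/21 = 4.8 and 1/8 = 12.5 points.

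**4. Distance from the relapse cut when treatment ends.** Remission is a MADRS below 10 and scores are whole numbers, so a remitter is at least 20 - 9 = 11 points below the cut. A patient with response only is at most 20 - 10 = 10 below it. A baseline of 30 halved leaves 20 - 15 = 5, and a baseline of 40 halved leaves 20 - 20 = 0. Part of any advantage for remitters is therefore built into the definitions.

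**5. Relapse rule against the visits.** The rule needs high scores in two successive weeks. The contacts supply one score a month. The only one-week rating in the text is the early termination MADRS, and it follows relapse or withdrawal; it is not stated to confirm a first high score.

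**The case against.** The plan does not say the percentage will be pooled. It names both groups, the hypothesis names the contrast, and a terse sentence might have been meant to cover two percentages. That is a possible reading. But the naming sentence identifies who is followed, and the next sentence announces no split, while the same section states its bipolar I/II split openly.

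A reader might infer that the whole comparison would be invented after the data are seen. The documents do not support that. Remission, response, the six-month window and the relapse cut are all defined, and the category of response without remission is already in use. What remains open is narrower: loss to follow-up and when response is judged.

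The split also will not settle the hypothesis, as the half-widths and power show. This stands, and it is why no test is proposed and the point is minor. The absence of intervals is general to the plan and not peculiar to relapse. Intervals are requested here because the groups are so small.

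On the relapse rule, a reader might infer that relapse can never be confirmed. That goes too far. The schedule of events is not in the text available for review, so contacts triggered by a high score cannot be excluded. The early termination MADRS also offers a one-week rating that could serve.

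**Conclusion.** The concern holds as a minor point. The stated analysis cannot address whether remitters hold their response better, and the relapse rule does not fit the monthly contacts given in the text. No primary result is affected.

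A split would be descriptive. The expected group sizes assume that the clinic's earlier rates carry over to this trial. The 25 to 47 point half-widths also rest on assumed relapse of 20% to 40%, since the documents give no relapse rate.

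A reader might take a lower relapse rate in remitters as evidence that reaching remission protects against relapse. The design does not support that. Remission is an outcome of treatment and not an assigned group, TMS stops when it is reached, other responders receive 30 to 35 sessions, follow-up care is left to the clinician, and response-only patients start nearer the cut.

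**What to change.** In the Secondary Efficacy Analysis, replace the relapse sentence with:

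> The percentage relapsing through six months will be reported separately for remitters (MADRS <10 during treatment) and for all other patients entering Phase III (response without remission), each with an exact (Clopper-Pearson) 95% interval, and with a Newcombe 95% interval for the difference; no test will be done. The denominator is all patients entering Phase III in each group, with the number lost to follow-up and MADRS at Phase III entry shown by group. The contrast is descriptive and an association, because TMS stops at remission and response-only patients enter closer to the cut of 20.

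Defining the second group as all other entrants also places a patient who met response and later lost it. The interval methods are named because the simple formula used above collapses to zero width within a group that has no relapses, such as 0/11.

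In the Phase III section, add:

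> A MADRS of 20 or above at a monthly contact triggers the one-week MADRS used at early termination, in person or by phone. Relapse is confirmed if that score is also 20 or above; if it is not, follow-up continues.

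This reads two successive weeks as two scores one week apart. If a full 14 days is meant, the text should say so. If no repeat rating is adopted, report the outcome as MADRS 20 or above at any monthly contact, under that name.

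**Cost.** The split needs only wording and data already collected. At the assumed 30%, confirmed relapses would number about 0.3 × 17 = 5.1 to 0.3 × 39 = 11.7, so about 5 to 12. For these, the rating is the early termination MADRS the plan already requires. High scores that are not confirmed add a few more. The main drawback is that the intervals will be wide and the comparison may be inconclusive.
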